9.1.4. Observational Period (Week 60 through Week 84)

At Week 72, Subjects will be followed for safety and PK and immunogenicity information, Subjects will be followed for safety, and maintenance of efficacy information during the observational period (Week 60 through Week 84) as per the [TIME AND EVENTS SCHEDULE](#).

9.1.5. Safety follow-up after Early Termination

For subjects who withdraw from study participation, every effort should be made to conduct final efficacy and safety assessments at 12 weeks after the last administration of the study drug, which are the same as Week 72.

9.2. Efficacy

9.2.1. Evaluations

Efficacy evaluations chosen for this study are consistent with those utilized to evaluate other therapies for palmoplantar pustulosis. Efficacy evaluations include:

- Palmoplantar Pustulosis Area and Severity Index (PPPASI)
- Palmoplantar Pustulosis Severity Index (PPSI)
- Physician's Global Assessment (PGA)

- Dermatology Life Quality Index (DLQI)
- 36-item short-form health survey (SF-36)
- EuroQOL five dimensions questionnaire (EQ-5D)
- Magnetic Resonance Imaging (MRI)
- Photographs

Efficacy assessments (PPPASI, PPSI, PGA) will be performed at the site by an efficacy assessor trained by the sponsor at the appropriate visits as outlined by the [TIME AND EVENTS SCHEDULE](#).

The PRO assessments will be completed at the site by subjects at the appropriate visits as outlined by the [TIME AND EVENTS SCHEDULE](#). All visit-specific PRO assessments during a visit should be conducted before any tests, procedures, or other consultations for that visit to prevent influencing subject perceptions.

9.2.1.1. Palmoplantar Pustulosis Area and Severity Index (PPPASI)

The PPPASI assesses the severity of palmoplantar pustulosis lesions and their response to therapy (see [Attachment 1](#)). In the PPPASI system, the palms and soles are divided into 4 regions: the right palm, left palm, right sole, and left sole, which account for 20%, 20%, 30%, and 30%, respectively, of the total surface area of the palms and soles. Each of these areas is assessed separately for erythema, pustules/vesicle and desquamation/scale, which are each rated on a scale of 0 to 4. The PPPASI produces a numeric score that can range from 0 to 72. A higher score indicates more severe disease.

9.2.1.2. Palmoplantar Pustulosis Severity Index (PPSI)

The PPSI assesses the severity of palmoplantar pustulosis lesions and their response to therapy with a score ranging from 0 to 12 (see [Attachment 2](#)). In the PPSI system, the more severely affected location (palms or soles) will be identified as the evaluation sites at screening. The identified site will be assessed at all subsequent visits. Evaluation sites are assessed separately for erythema, pustules/vesicle and desquamation/scale, for the most severe skin lesion rated on a scale of 0 to 4.

9.2.1.3. Physician's Global Assessment (PGA)

The PGA documents the Physician's Global Assessment of the subject's palmoplantar overall skin lesions status (see [Attachment 3](#)). The patient's palmoplantar pustulosis is assessed as clear (0), almost clear (1), mild (2), moderate (3), severe (4), or very severe (5).

9.2.1.4. Patient-Reported Outcome (PRO)

9.2.1.4.1. Dermatology Life Quality Index (DLQI)

The DLQI is a dermatology-specific quality of life instrument designed to assess the impact of the disease on a subject's quality of life. It is a 10 item PRO questionnaire that, in addition to evaluating overall quality of life, can be used to assess 6 different aspects that may affect quality

of life: symptoms and feelings, daily activities, leisure, work or school performance, personal relationships, and treatment. The DLQI produces a numeric score that can range from 0 to 30. A higher score indicates more severe disease.

9.2.1.4.2. 36-item short-form health survey (SF-36)

The SF-36 consists of 8 multi-item scales: limitations in physical functioning due to health problems, limitations in usual role activities due to physical health problems, bodily pain, general mental health (psychological distress and well-being), limitations in usual role activities due to personal or emotional problems, limitations in social functioning due to physical or mental health problems, vitality (energy and fatigue), and general health perception. A physical component summary (PCS) scores and mental component summary (MCS) score can be derived. The concepts measured by the SF-36 are not specific to age, disease or treatment group, allowing comparison of relative burden of different diseases and the relative benefit of different treatments.

9.2.1.4.3. EuroQOL five dimensions questionnaire (EQ-5D)

The EQ-5D is designed for self-completion by subjects and consists of 2 pages - the EQ-5D descriptive system and the EQ visual analog scale (EQ VAS). The EQ-5D descriptive system comprises the following 5 dimensions: mobility, self-care, usual activities, pain/discomfort and anxiety/depression. Each dimension has 5 levels: no problems, slight problems, moderate problems, severe problems and unable. The EQ VAS records the respondent's self-rated health on a vertical, visual analog scale where the endpoints are labeled 'Best imaginable health state' (score of 100) and 'Worst imaginable health state' (score of 0). EQ-5D descriptive system can be converted into a single summary EQ-5D Index. EQ-5D index scores in this analysis will be derived based on the Japanese population.

9.2.1.5. Magnetic Resonance Imaging (MRI)

MRI image of Pustulotic Arthro-Osteitis (PAO) will be taken and should be provided to the sponsor (only for subjects with PAO at screening). MRI image of PAO will be centrally evaluated. Subjects with contraindication in MRI image (eg, claustrophobia, metal implant) are not allowed to undergo MRI. The details will be provided in a separate PAO Central Evaluation charter.

9.2.1.6. Photographs

Overview photographs of the palms and soles will be taken at a subset of study sites in patients who provide an additional consent. See Trial Center File for photography instructions.

9.2.2. Endpoints

Primary Endpoint

Change from baseline in PPPASI total score at Week 16, comparing the CNTO 1959 groups and the placebo group.

Major Secondary Endpoints

- Change from baseline in PPSI total score at Week 16
- Proportion of subjects who achieve a PPPASI-50 at Week 16

Other Secondary Endpoints

- Change from baseline in PPPASI total score over time
- Change from baseline in PPSI total score over time
- Proportion of subjects who achieve a PPPASI-50 over time
- Proportion of subjects who achieve a PPPASI-75, PPPASI-90, PPPASI-100 over time.
- Proportion of subjects who achieve a PPSI-50, PPSI-75, PPSI-90, PPSI-100 over time.
- Change from baseline in PGA score over time.
- Proportion of subjects who achieve a PGA score of cleared (0) or minimal (1) over time.
- Proportion of subjects who achieve a PGA score of cleared (0) or minimal (1) and have at least a 2-grade improvement from baseline over time.
- Change from baseline in DLQI score over time.
- Change from baseline in SF-36 score over time.
- Change from baseline in EQ-5D score over time.

Exploratory Endpoints

- Change from baseline in EQ-5D score in PAO subjects over time.

9.3. Pharmacokinetics and Immunogenicity

Blood samples will be collected for the measurement of serum CNTO 1959 concentrations and detection of antibodies to CNTO 1959 at the timepoints presented in the [TIME AND EVENTS SCHEDULE](#). Blood samples will also be collected at the final visit from subjects who terminate study participation early.

9.3.1. Evaluations

Venous blood samples of approximately 6 mL will be collected for determination of serum concentrations of CNTO 1959 and antibodies to CNTO 1959.

Samples will be used to evaluate the pharmacokinetics, as well as the immunogenicity of CNTO 1959 (antibodies to CNTO 1959). Venous blood samples will be collected and serum samples will be divided into 3 aliquots (1 aliquot for CNTO 1959 concentration, 1 aliquot for antibodies to CNTO 1959, and 1 aliquot as back-up samples may be used as spare samples for sample loss for CNTO 1959 concentration and antibodies to CNTO 1959).

Samples collected for analyses of CNTO 1959 serum concentration and antibody to CNTO 1959 may additionally be used to evaluate safety or efficacy aspects that address concerns arising during or after the study period for the evaluation of relevant biomarkers.

At visits where serum concentration and antibodies to CNTO 1959 will be evaluated, 1 blood draw of sufficient volume can be used.

Samples must be collected at study visits before study drug is administered. The exact dates and times of blood sampling must be recorded in the laboratory requisition form.

See the Laboratory Manual for further information regarding collection, handling, and shipment of biological samples.

9.3.2. Analytical Procedures

Serum samples will be analyzed to determine concentrations of serum CNTO 1959 using a validated, specific, and sensitive electrochemiluminescence immunoassay (ECLIA) method by the sponsor's bioanalytical facility or under the supervision of the sponsor. The sponsor, or its designee, under conditions in which the subjects' identity remains blinded, will assay these samples.

9.3.3. Pharmacokinetic Parameters

If feasible, the apparent clearance (CL/F) and apparent volume of distribution (V/F) will be estimated using a nonlinear mixed effects modeling (NONMEM) approach.

9.3.4. Immunogenicity Assessments Antibodies to CNTO 1959

The presence of antibodies to CNTO 1959 in serum will be detected using a validated ECLIA method by the sponsor's bioanalytical facility or under the supervision of the sponsor.

Serum samples that test positive for antibodies to CNTO 1959 will be further characterized to determine if antibodies to CNTO 1959 could neutralize the biological effects of CNTO 1959 in vitro (ie, neutralizing antibodies [NAbs] to CNTO 1959).

9.4. Pharmacokinetic/Pharmacodynamic Evaluations

If data permit, the relationships between serum CNTO 1959 concentration and efficacy may be analyzed graphically. If any visual trend is observed, a suitable population PK/PD model may be developed to describe the exposure-response relationship.

9.5. Biomarkers

Biomarker samples will include serum according to the [TIME AND EVENTS SCHEDULE](#). Serum samples will be analyzed for the presence of serum markers related to Palmoplantar Pustulosis and/or inflammation. For biomarkers, known proteins related to Palmoplantar Pustulosis or CNTO 1959 (for example, IL-17, IL-23) will be measured after completion of the study. Instructions for the collection and shipment of these samples can be found in the appropriate Laboratory Manual.

9.6. Safety Evaluations

Safety and tolerability will be assessed by collecting information on AEs, Clinical Laboratory Testing ([Attachment 10](#)), ECG, vital signs (axillary temperature, pulse rate, blood pressure),

physical examinations, concomitant medication review, injection-site evaluations, allergic reactions, and early detection of TB (TB evaluation).

Any clinically relevant changes occurring during the study must be recorded on the Adverse Event section of the eCRF.

Any clinically significant abnormalities persisting at the end of the study/early withdrawal will be followed by the investigator until resolution or until a clinically stable endpoint is reached, or when investigators determine follow-up to be unnecessary.

The study will include the following evaluations of safety and tolerability according to the time points provided in the [TIME AND EVENTS SCHEDULE](#):

Adverse Events

Adverse events will be reported by the subject (or, when appropriate, by a caregiver, surrogate, or the subject's legally-acceptable representative) for the duration of the study. Adverse events will be followed by the investigator.

Clinical Laboratory Tests

Blood samples for serum chemistry, hematology and lipid and a random urine sample for urinalysis will be collected. The investigator must review the laboratory report, document this review, and record any clinically relevant changes occurring during the study in the AE section of the eCRF. The laboratory reports must be filed with the source documents.

The following tests will be performed:

- Hematology Panel

-Hemoglobin	-WBC with differential ^a
-Hematocrit	-Lymphocytes
-RBC	-Monocytes
-Platelets	-Neutrophils
	-Eosinophils
	-Basophils

a. If other hematocytes are detected, then their result will be provided.

- Serum Chemistry Panel

-Albumin	-Chloride
-Alkaline phosphatase	-Creatinine
-ALT/SGPT	-Glucose
-AST/SGOT	-HbA1c
-Total CO ₂	-Potassium
-Total bilirubin	-Total protein
-Urea	-Sodium
-Calcium	- hsCRP

- Lipid Panel

-Total cholesterol	-Total cholesterol to HDL ratio
-LDL	-Triglycerides
-HDL	

- Serology/other screening

-HBV ^{b,c}	-IGRAs (T-SPOT.TB test or QuantiFERON-TB Gold)
-Antibodies to HCV	-Serum β -hCG, Qualitative ^d
-Antibodies to HIV	-FSH ^e
-Antibodies to HTLV-1	

b. Includes HBV serology and HBV DNA testing. (See [Attachment 10](#) for criteria of HBV DNA quantitative test required)

c. If core antibody (anti-HBc) and/or surface antibody (anti-HBs) are positive and the HBV DNA test is negative, HBV DNA quantitation should be monitored at least every 3 months or shorter.

d. Woman of childbearing potential only.

e. Necessary female subject only. (see Inclusion Criterion 7)

Electrocardiogram (ECG)

A supine 12-lead ECG will be performed at screening and at Weeks 16, 52 and 72, as specified in the [TIME AND EVENTS SCHEDULE](#). A full 12-lead ECG will be recorded and the data will be stored in digital format and will be read at a central site as per the ECG Manual.

Vital Signs

Measurement of vital signs (axillary temperature, pulse rate, blood pressure) will be performed at the time points specified in the [TIME AND EVENTS SCHEDULE](#).

If any clinically significant changes in vital signs are noted, they must be reported as AEs and followed to resolution, or until reaching a clinically stable endpoint.

Physical Examination

Physical examinations will be performed by the investigator. The timepoints of these examinations are specified in the [TIME AND EVENTS SCHEDULE](#).

Any abnormalities or changes in severity noted during the review of body systems should be documented in the source document and recorded on the AE page of the eCRF.

A new, clinically significant finding (in the opinion of the investigator) not noted at screening must be captured as an AE. In addition, resolution of any abnormal findings during the study will be noted in the source document and in the eCRF.

Height and Weight

Height and weight will be measured at visits noted in the [TIME AND EVENTS SCHEDULE](#). Subjects will be instructed to remove shoes and outdoor apparel and gear.

Injection Site Evaluation

An injection site reaction is any unfavorable or unintended sign that occurs at the study drug injection site. All subjects will be carefully observed at the study site for at least 30 minutes after the SC injection of study drug for symptoms of an injection-site reaction. If an injection site reaction is observed, the subject should be treated at the investigator's discretion. Any adverse reaction (eg, pain, erythema, and/or induration) should be noted on the AE page of the eCRF.

Allergic Reactions

The sponsor will proactively monitor reported AEs and query the site, if necessary, to capture anaphylactic reaction/serum sickness events in eCRFs.

Early Detection of Active Tuberculosis

To aid in the early detection of TB reactivation or new TB infection during study participation, subjects must be evaluated for signs and symptoms of active TB at scheduled visits. The following series of questions are suggested for use during the evaluation:

- “Have you had a new cough of > 14 days’ duration or a change in a chronic cough?”
- “Have you had any of the following symptoms: Persistent fever? Unintentional weight loss? Night sweats?”
- “Have you had close contact with an individual with active TB?” (If there is uncertainty as to whether a contact should be considered “close,” a physician specializing in TB should be consulted.)

If the evaluation raises suspicion that a subject may have TB reactivation or new TB infection, an immediate and thorough investigation should be undertaken, including, where possible, consultation with a physician specializing in TB.

Investigators should be aware that TB reactivation in immunocompromised subjects may present as disseminated disease or with extra pulmonary features. Subjects with evidence of active TB should be referred for appropriate treatment.

Subjects who experience close contact with an individual with active TB during the conduct of the study must have a repeat chest radiograph (both posterior-anterior and lateral views,

substitutable with chest CT), a repeat IGRA, and, if possible, referral to a physician specializing in TB to determine the subject's risk of developing active TB and whether treatment for latent TB is required.

If the IGRA result is indeterminate, the test should be repeated. Subjects should be encouraged to return for all subsequent scheduled study visits according to the protocol.

Pregnancy Testing

Urine pregnancy testing is required for all women of childbearing potential at all study drug administration visit. Pregnancy tests must be completed and the result must be negative before the administration of any study drug for that visit. All pregnancy test results must be recorded in study source documents.

9.7. Sample Collection and Handling

The actual dates and times of sample collection must be recorded in the eCRF or laboratory requisition form. Refer to the [TIME AND EVENTS SCHEDULE](#) for the timing and frequency of all sample collections.

Instructions for the collection, handling, storage, and shipment of samples are found in the Laboratory Manual that will be provided. Collection, handling, storage, and shipment of samples must be under the specified, and where applicable, controlled temperature conditions as indicated in the Laboratory Manual.

10. SUBJECT COMPLETION/WITHDRAWAL

10.1. Completion

A subject will be considered to have completed the study if he or she has completed assessments at Week 60 of the treatment phase. Subjects who prematurely discontinue study treatment for any reason before completion of the treatment phase will not be considered to have completed the study.

10.2. Discontinuation of Study Treatment

If a subject's study treatment must be discontinued before the end of the treatment regimen, this will not result in automatic withdrawal of the subject from the study.

A subject's study treatment should be discontinued if:

- The investigator believes that for safety reasons (eg, adverse event) it is in the best interest of the subject to discontinue study treatment.
- The subject becomes pregnant.
- The subject is diagnosed with a malignancy, with the exception of no more than 2 localized basal cell skin cancers that are treated with no evidence of recurrence or residual disease.
- The subject is deemed ineligible according to the following TB screening criteria:

-
- A diagnosis of active TB is made.
 - A subject has symptoms suggestive of active TB based on follow-up assessment questions and/or physical examination, or has had recent close contact with a person with active TB, and cannot or will not continue to undergo additional evaluation.
 - A subject undergoing evaluation has a chest radiograph with evidence of current active TB and/or a positive IGRA result, unless active TB can be ruled out and appropriate treatment for latent TB can be initiated prior to the next administration of study drug and continued to completion. Indeterminate IGRA results should be handled as in Section 9.1.2, Screening Phase. Subjects with persistently indeterminate IGRA results may continue without treatment for latent TB if active TB is ruled out, their chest radiograph (both posterior-anterior and lateral views, substitutable with chest CT) shows no abnormality suggestive of TB (active or old, inactive TB) and the subject has no additional risk factors for TB as determined by the investigator and medical monitor.
 - A subject receiving treatment for latent TB discontinues this treatment prematurely or is noncompliant with the therapy.
- The subject initiates a protocol-prohibited therapy (unless previously agreed to by the medical monitor).
 - The subject withdraws consent for administration of study drug.
 - The subject is unable to adhere to the study visit schedule or comply with protocol requirements.
 - The subject develops a severe allergic reaction such as bronchospasm with wheezing and/or dyspnea requiring ventilatory support, or symptomatic hypotension that occurs following a study drug administration.
 - The subject has a reaction resulting in myalgia and/or arthralgia with fever and/or rash (suggestive of serum sickness and not representative of signs and symptoms of other recognized clinical syndromes) occurring 1 to 14 days after an injection of study drug. These may be accompanied by other events including pruritus, facial, hand, or lip edema, dysphagia, urticaria, sore throat, and/or headache.

Discontinuation of study treatment should be considered for subjects who develop a serious or opportunistic infection, congestive heart failure, demyelinating disease, lupus-like syndrome, cytopenias (including pancytopenia) and liver abnormalities.

Discontinuation of study treatment should also be considered for subjects who have shown no response with up to 28 weeks of treatment.

If a subject discontinues study treatment before the end of the double-blind treatment phase, every effort should be made to conduct final efficacy and safety assessments at 12 weeks after the last administration of the study drug, which are the same as Week 72.

Subjects who decide to discontinue study drug administration must be interviewed by the investigator to determine if a specific reason for discontinuing study drug can be identified. Subjects should be explicitly asked about the contribution of possible AEs to their decision to discontinue study drug; investigators should confirm that any AE information elicited has been

documented. If a subject elects to discontinue study drug due to an AE, the event should be recorded as the reason for study drug discontinuation, even if the investigator's assessment is that the AE would not require study drug discontinuation. The reason for study drug discontinuation must be documented in the eCRF and in source documents. Study drug assigned to a subject who discontinues may not be assigned to another subject.

10.3. Withdrawal From the Study

A subject will be withdrawn from the study for any of the following reasons:

- Lost to follow-up
- Withdrawal of consent
- Death
- The investigator or sponsor believes (eg, that for safety or tolerability reasons such as an AE) it is in the best interest of the subject to discontinue treatment.
- The investigator deems the subject should initiate the protocol-prohibited medications/treatment due to lack of efficacy or other reason.

If a subject is lost to follow-up, every reasonable effort must be made by the study site personnel to contact the subject and determine the reason for discontinuation/withdrawal. The measures taken to follow up must be documented.

When a subject withdraws before completing the study, the reason for withdrawal is to be documented in the eCRF and in the source document. Study drug assigned to the withdrawn subject may not be assigned to another subject. Subjects who withdraw will not be replaced.

If a subject withdraws from the study before the end of the double-blind phase, early termination assessments (which are the same as Week 72) should be obtained wherever possible. The subject should be encouraged to conduct the safety follow-up visits for up to 12 weeks after the last dose of study drug. If a subject elects to terminate participation in the study, every effort should be made to schedule an early termination visit as soon as possible.

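### Sections 10.2 and 10.3 give opposite consequences for the same safety stop, so some Week 16 primary scores can be lost avoidably

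*Protocol*

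**What the plan says.** **Section 10.2 (Discontinuation of Study Treatment).** If treatment must stop early, "this will not result in automatic withdrawal of the subject from the study". The first listed reason is the investigator's belief that "for safety reasons (eg, adverse event) it is in the best interest of the subject to discontinue study treatment". A later reason is "The subject initiates a protocol-prohibited therapy (unless previously agreed to by the medical monitor". For anyone who stops before the end of the double-blind phase, "every effort should be made to conduct final efficacy and safety assessments at 12 weeks after the last administration of the study drug".

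**Section 10.3 (Withdrawal From the Study).** The list opens with "A subject will be withdrawn from the study for any of the following reasons". The fourth bullet is the investigator's or sponsor's belief, "eg, that for safety or tolerability reasons such as an AE) it is in the best interest of the subject to discontinue treatment". The fifth is "The investigator deems the subject should initiate the protocol-prohibited medications/treatment due to lack of efficacy or other reason". If a subject ends participation, "every effort should be made to schedule an early termination visit as soon as possible".

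**Section 11.3.3 (Primary Analysis).** All randomized subjects are analysed as assigned, with an MMRM over Weeks 2, 4, 8, 12 and 16. Nothing is imputed, and missing scores are assumed missing at random.

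**The concern.** The fourth bullet of 10.3 is about ending treatment, but it sits in a list whose consequence is leaving the study. It wholly covers the first bullet of 10.2, where the consequence is the opposite. Two sites facing the same adverse event before Week 16 could each follow the protocol, one keeping the subject and the other removing the subject.

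The prohibited-therapy bullets overlap less directly. Section 10.2 concerns a subject who has started such therapy and allows an exception by the medical monitor. Section 10.3 concerns an investigator who judges that it should be started.

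At stake is the Week 16 PPPASI score of randomized subjects. An analysis plan can choose how to treat a score, but it cannot recover one that was never taken, nor settle which section a site followed.

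**Working it through.** **1. The two rules side by side**

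| | Section 10.2 | Section 10.3 |
|---|---|---|
| Who decides | investigator | investigator or sponsor |
| Ground | safety, subject's best interest | safety or tolerability, subject's best interest |
| What is stopped | study treatment | treatment |
| Consequence | no automatic withdrawal | withdrawal, stated as mandatory |

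The word automatic in 10.2 does not reconcile them, because 10.3 leaves no discretion once the belief is held.

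**2. Is continued attendance stated elsewhere?**

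- Section 5 tells subjects whose code was broken to keep returning for evaluations. This covers that group only.
- Section 9.6 encourages return for later visits, but within the tuberculosis text.
- Sections 9.1.1 and 9.1.3 set the visit schedule without exempting subjects off treatment, so they can be read to require attendance.
- Against that reading, 10.2 calls the 12-week assessment final.

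No sentence expressly covers an ordinary adverse-event or best-interest stop.

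**3. Does the 12-week assessment supply a Week 16 score?**

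Inputs: doses before Week 16 are at Weeks 0, 4 and 12 (section 3.1). The visit allowance is ±7 days from Week 8 onward (Time and Events Schedule). I assume dosing on the nominal day and apply the same ±7 days to the 12-week assessment.

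Week 16 window: 16 × 7 = 112, so days 105–119. Week 12 window: 12 × 7 = 84, so days 77–91. Assessment day = (last dose week + 12) × 7.

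| Last dose | Assessment day | Window | In Week 16 window? | Week 12 score? |
|---|---|---|---|---|
| Week 0 | 84 | 77–91 | no | yes, if this assessment is held (same days as the Week 12 window) |
| Week 4 | 112 | 105–119 | yes | not supplied by this assessment |
| Week 12 | 168 | 161–175 | no | yes, scored before the Week 12 injection (schedule footnote c) |

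The early termination visit in 10.3 is not tied to Week 16. It helps only if it falls on day 105 or later. A stop decided at the Week 16 visit itself costs nothing, because scoring precedes injection.

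**4. Power**

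Section 11.2 uses a two-sample t-test with difference 5.5, SD 8.1 and two-sided alpha 0.05. With n per group, noncentrality = 5.5 / (8.1 × √(2/n)) and df = 2n − 2.

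- Plan's own figure, n = 47: 5.5 / (8.1 × 0.2063) = 3.29, power 90.3% (plan: 90%). Reproduced.
- n = 50: 5.5 / (8.1 × 0.2000) = 3.40, power 91.9%.
- n = 45 (10% of 50 lost): 5.5 / (8.1 × 0.2108) = 3.22, power 89.0%.
- n = 40 (20% lost): 5.5 / (8.1 × 0.2236) = 3.04, power 85.1%.

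The loss rates are assumptions, since the protocol gives none. They overstate the cost, because the MMRM uses earlier visits from subjects without a Week 16 score and the sample size may rise to 75 per group.

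**The case against.** The best defence is that this is a drafting overlap with narrow effect. Several parts of it stand.

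- **Earlier data remain.** In both cases where the 12-week assessment misses Week 16, a Week 12 score normally exists, one visit before the endpoint, and the MMRM uses it. The main exception is an early termination visit before Week 12 with no 12-week assessment.
- **Treatment failures are already assigned to the analysis plan.** Section 11.3.2 covers stops for lack of efficacy or worsening disease, and prohibited therapy that could improve it. Stops for other adverse events without such therapy fall outside that rule.
- **Losses may be few.** Section 11.2 tabulates 24 + 25 = 49 phase 2 subjects at Week 16, against about 50 planned (section 1.1). The number randomized and any imputation are not stated, so this is only suggestive.
- **Supporting signs are weak.** The completion definition in 10.1 is administrative. The LOCF sentence in 11.3.3 anticipates scores missing after a treatment stop but does not say that visits end.

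A reader might also infer more than the text supports:

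- That every subject stopped for lack of efficacy leaves the study. Section 10.3 has no such rule. Its last bullet needs a judgement that prohibited therapy should start, and the non-response stop after up to 28 weeks sits in 10.2 as a treatment matter.
- That half of early stops lose the Week 16 score, because the missed intervals (Weeks 0–4 and 12–16) make up 8 of 16 weeks. That is calendar time, not a share of subjects.
- That the primary result is biased or the trial underpowered. Nothing in the document shows either.

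What the defence does not remove is the contradiction itself, or the fact that following 10.3 as written can end collection before the primary time point.

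**Conclusion.** The contradiction between 10.2 and 10.3 is explicit and should be corrected. Its consequence is limited: some Week 16 PPPASI scores may be lost avoidably, for reasons that may relate to outcome, and the primary analysis must then rely on missing at random for them. How many are affected, and in which direction any bias would run, cannot be derived from the protocol.

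The case rests on consistent conduct and complete primary data. Power is a minor matter: 91.9% with 50 per group, and 89.0% under an assumed 10% crude loss. The timing result assumes nominal dosing days and a ±7-day allowance on the 12-week assessment.

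**What to change.** In section 10.3:

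- Reword the fourth bullet so that it applies only when continued participation in the study, not treatment, is judged to be against the subject's interest. Deleting it outright would remove the stated ability to withdraw a subject for safety.
- Make the prohibited-therapy bullet a treatment discontinuation under 10.2.

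Add to section 10.2: *Subjects who discontinue study treatment before Week 16 and have not died, withdrawn consent to follow-up or been withdrawn because continued participation is unsafe will attend the scheduled visits with PPPASI, PPSI and PGA through Week 16, in addition to the assessment 12 weeks after the last dose.*

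The cost is a wording amendment and at most the remaining scheduled visits (Weeks 2, 4, 8, 12 and 16) for the subjects who stop early. Some Week 16 scores will then follow prohibited therapy. The treatment-failure rules that section 11.3.2 leaves to the SAP must say how those scores are used.
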